## **E. HUMAN SUBJECTS**

### **Monitoring and Human Subjects Protection**

#### Risks to Human Subjects

##### **1. Human Subject Involvement:**

Ambulatory moderately affected DM1 patients between the ages of eighteen and eighty will be evaluated during this clinical trial. The inclusion/ exclusion criteria are listed in the patient selection section above.

Nonambulatory patients have been excluded because in our experience the majority of non-ambulatory patients have advanced weakness in the arms and legs, especially in the flexors of the fingers and the intrinsic hand muscles. Such severe weakness will prevent this group of patients from participating in the assessment of myotonia (grip myotonia testing, repeated rapid contraction and extension of the fingers). These patients are also unable to perform 6 minute walk testing which is the primary end point used to assess efficacy of treatment for this study.

##### **2. Sources of Research Material:**

The sources of our research material are the data collected from the history and physical examination of each patient, and from the results of 6 minute walk testing, myotonia testing, muscle testing, blood and urine specimen analyses. The material is solely for research purposes. Patients will be asked to give permission for investigators to examine existing medical records and to determine their eligibility.

All data forms will contain the initials of each study subject and their assigned study number.

### 3. Potential Risks:

The risk category of this study is greater than minimal.

Mexiletine is approved by the FDA as an alternative treatment for symptomatic ventricular arrhythmias. The dosage selected for use in this study is in the low therapeutic range. Toxic side effects of mexiletine occur with greater frequency at higher dosages required to control arrhythmias and neuropathic pain. These dosages are typically two to three times higher than the dosages used in the present study. Patients taking these higher dosages of mexiletine (600-3200 mg/day) have a significantly increased incidence of upper gastrointestinal distress, 41%, lightheadedness and tremor, 12.5%. These symptoms are dose related, generally not serious, and disappear after dose reduction or discontinuation of treatment. No patient in our study will receive a dose of mexiletine greater than 450 mg a day.

A recent study which included 9 patients with DM1 has demonstrated that the relatively low dosage of mexiletine proposed for use in the present study is effective and has greater efficacy than other commonly used antimyotonia drugs, such as, dilantin, disopyramide, and tocainide. In addition, there were no severe side effects, worsening of heart block, or worsening of bundle branch block in our previous mexiletine crossover study of DM1 patients evaluating two low to moderate dosages [150 mg three times daily and 200 mg three times daily].

We anticipate that treatment with mexiletine will reduce or eliminate myotonia in our patients, and that they will experience few if any side effects at the dosage we have proposed.

There is a small risk of bruising from blood draws and muscle soreness from the quantitative myometry (QMT), manual muscle testing (MMT), maximum voluntary isometric contraction testing, and functional tests. Dual energy x-ray absorptiometry (DEXA) uses 0.5-1.0 mREM which is only a fraction of that used in a routine chest x-ray (20-30mREM) and is considered to pose to significant risk. There is minimal risk of transient discomfort from direct irritation to the nerve associated with the electrical stimulation during the repetitive stimulation test (measuring duration of myotonia).

Questionnaires, although we believe their content is benign, may produce mild emotional stress.

### Adequacy of Protection Against Risks

#### 1. Recruitment and Consent Procedures:

Patients will be recruited from the University of Rochester Neuromuscular Disease Center and from the list of patients who have received permission from their regular physicians to participate in our ongoing research studies of DM1. Both sexes will be recruited, as will members of all minorities. Interested potential subjects will be contacted by phone by the study coordinator and questioned about their health status.

Interested potential subjects who report no history of medical or psychiatric disease and a previous diagnosis of DM1 will be asked to come to the Clinical Research Center (CRC) for a screening visit. Women will be recruited only if they are using adequate birth control measures, or are postmenopausal, or have had a tubal ligation, or have had a hysterectomy.

When possible, subjects will be provided with a copy of the consent form for their review prior to the screening visit. Informed consent will be obtained by the principal investigator or study coordinator after details of the study and its requirements have been presented, and there has been an opportunity for the subject to ask questions. Consent will be obtained only after complete information has been provided to the participant about the purpose of the study, the procedures, risks, benefits, contact persons, compensation, and care for injury, and voluntary participation. The subject study personnel obtaining consent will sign the IRB approved consent form. The subject will receive a copy of the consent form after it has been signed. The original will be retained in the files of the investigator.

## 2. Procedures for Protecting Against or Minimizing Risks:

All subjects will be monitored closely by the CRC nursing staff and investigators during the procedures to prevent and minimize any potential risks or discomfort. The nursing staff and study personnel will receive in-service training regarding these procedures. Each participant will be asked to report any continuing discomfort caused by any of the performed procedures.

If a woman is pregnant, she will not continue in the study.

Safety data receive appropriate review by our DSMB and independent medical monitor and will be given to the data manager who will keep the records in a locked file cabinet and maintain their confidentiality. In all databases and reports, subjects will be identified by an ID number.

In addition to the assessments during each evaluation on the CRC adverse events will be monitored during telephone calls at about 2 week intervals. The laboratory studies will provide additional means to detect any evidence of major organ toxicity.

Patients will be withdrawn from the study if intolerable side effects or severe adverse events, as determined by the PI, are identified. Patients who cannot tolerate the medication or procedures, have surgery or other illnesses which affect the evaluations will have the drug discontinued. Patients may withdraw at any time. All withdrawals will be reported to the statistical center, DSMB, and safety monitor within 24 hours. Occurrence of a serious adverse event must be reported to the IRB and principal investigator, DSMB, and independent medical monitor within 24 hours.

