### **Withdrawal/ Discontinuation/ Dosage Reduction:**

Patients will have the option of withdrawing from the study at any time. Patients may also be withdrawn because of an inability to comply with study procedures (e.g., because of significant surgery or medical illness). If a patient experiences intolerable adverse events, the dosage may be reduced by one level (e.g. from three times a day dosing to twice a day dosing). Patients who experience intolerable adverse events requiring withdrawal of study medication or who require treatment with exclusionary medications will continue to be followed according to the protocol, if the patient is willing. Primary statistical analyses will be performed according to the intention-to-treat principle and will utilize all patient data collected.

All patient withdrawals, dosage reductions, treatment discontinuations, and treatment with exclusionary medications will be carefully documented on case report forms.

In case of a medical emergency, the principal investigator will contact the pharmacy and become unblinded to the patient's treatment assignment.

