The primary analyses will be performed according to the intention-to-treat principle and will include all randomized subjects. Every effort will be made to retain subjects in this study and to collect all data at every visit. If a subject cannot tolerate or refuses to continue taking study medication, we will continue to follow and evaluate that subject if he/she is willing. If a subject drops out, attempts will be made to bring the subject in for a final evaluation. Compliance with trial procedures, dropouts/dropins, and reasons for subject withdrawal will be carefully tracked throughout the study. The repeated measures analysis of covariance model above uses maximum likelihood to estimate the parameters of interest (treatment effects) using available data from all subjects. A key assumption underlying this analysis is that the missing data are “missing at random” (MAR), i.e., the probability that responses are missing for a subject depends only on the set of observed data for that subject and not on the specific missing values that were not obtained.

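### One Human Subjects sentence removes patients with intolerable side effects from the study, while the rest of the plan reduces or stops the drug and keeps following them

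*Combined protocol and SAP*

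**What the plan says.** Three places in the protocol deal with patients who cannot tolerate study drug.

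- **Human Subjects, Procedures for Protecting Against or Minimizing Risks.** "Patients will be withdrawn from the study if intolerable side effects or severe adverse events, as determined by the PI, are identified". The next sentence reads: "Patients who cannot tolerate the medication or procedures, have surgery or other illnesses which affect the evaluations will have the drug discontinued".
- **Withdrawal/ Discontinuation/ Dosage Reduction.** "If a patient experiences intolerable adverse events, the dosage may be reduced by one level". If the drug has to stop: "Patients who experience intolerable adverse events requiring withdrawal of study medication or who require treatment with exclusionary medications will continue to be followed", provided the patient is willing. The section also allows removal from the study on a different ground: "Patients may also be withdrawn because of an inability to comply with study procedures".
- **Statistical Analyses.** "If a subject cannot tolerate or refuses to continue taking study medication, we will continue to follow and evaluate that subject", again if willing. For those who leave anyway: "If a subject drops out, attempts will be made to bring the subject in for a final evaluation".

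Two other sections bear on the reading. Evaluation of safety and tolerability has the principal investigator decide, for more serious side effects, between a lower dose and stopping the agent. Analysis of Safety Outcomes and Subject Disposition summarizes subjects who leave the study separately from those who stop the drug early. In this plan the two are different events.

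**The concern.** For one trigger, intolerable side effects, the protocol gives two instructions that cannot both be followed. The sentence in the risk section is mandatory and provides for no further visits. The other sections provide for those visits, and no section says which rule prevails. The risk section is also one that staff may well consult when a patient has an adverse event.

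The primary analysis is by intention to treat in all randomized subjects, with the six-minute walk at Month 6 as the endpoint. A patient taken out of the study has no Month 6 value, and perhaps no Month 3 value. The model then fills the gap as if that patient had gone on like the others in the arm with the same earlier data. If patients who stop mexiletine lose its benefit, that is too favourable and the Month 6 effect is overstated. These losses are avoidable, because the rest of the plan already commits to collecting the data.

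**Working it through.** **Inputs.** From Sample Size Considerations: effect 183 ft, SD 190 ft, 18 per group raised to 20 for 10% withdrawal. The 10% is withdrawal for any cause, so 2 of 20 per arm serves as an upper case for intolerance. Assumptions, because the documents give no figures: patients off mexiletine walk as placebo patients do, and the Month 3–Month 6 correlation is 0.5 or 0.8.

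**The plan's own figure.** A two-sample t-test with 183 ft, SD 190 ft and 18 per group has power 0.80 at a two-sided 5% level (assumed, since the primary power statement gives none). It also has 0.80 at the final-analysis level of 0.049. Allowing for withdrawal, 18/(1 − 0.10) = 20. Both figures reproduce.

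**Standard error of the Month 6 difference**, 190 × √(2/n):

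- n = 18: 63.3 ft
- n = 19: 61.6 ft
- n = 20: 60.1 ft

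**Overstatement when k of 20 mexiletine patients are lost.** If Month 3 is missing, or was seen while still on drug, the model predicts the full 183 ft benefit for a patient who in truth has none. The bias is 183 × k/20.

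- k = 1: 183 × 1/20 = 9.15 ft; 9.15/61.6 = 0.15 SE
- k = 2: 183 × 2/20 = 18.3 ft; 18.3/63.3 = 0.29 SE

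If Month 3 was seen off drug, the model already sees part of the loss and the bias shrinks to 183 × (k/20) × (1 − b). The slope b equals the correlation when the two visits have equal spread.

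| Lost on mexiletine | b = 0.5 | b = 0.8 |
|---|---|---|
| 1 | 4.6 ft | 1.8 ft |
| 2 | 9.2 ft | 3.7 ft |

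Simulated change scores (20,000 runs, k missing at Month 6 in each arm, maximum-likelihood estimate minus full-follow-up estimate) agree:

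- Month 3 missing: 9.1 and 18.2 ft for k = 1 and 2
- Month 3 seen on drug: 9.1 and 18.3 to 18.4 ft
- Month 3 seen off drug: 4.5 and 9.1 ft at 0.5; 1.8 and 3.8 ft at 0.8

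With no drug effect and k = 2 (5,000 runs), the mean estimates were 0.3 ft with full follow-up and 0.7 ft from the model. With a simulation error of 0.9 ft, this is no bias.

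**Precision.** With two losses per arm and Month 3 also missing, full follow-up lowers the SE from 63.3 to 60.1 ft. If Month 3 is seen, the repeated-measures model borrows from it, and the starting SE is about 190 × √(2 × [(1 − r²)/18 + r²/20]). That is 62.5 ft at r = 0.5 and 61.3 ft at r = 0.8. The gain is then only 2.4 or 1.2 ft, before counting the extra spread that off-drug patients add.

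**The case against.** The best defence is that the plan settles the matter elsewhere. The section devoted to withdrawal and dose reduction, the statistical section, the safety-evaluation section and the next sentence of the risk section itself all speak of reducing or stopping the drug. The odd sentence may be loose wording, and it leaves the call to the principal investigator. Few patients may be affected: Potential Risks reports no severe side effects in the earlier mexiletine crossover study, and the interim-analysis section says both seven-week trials finished without significant adverse events. The attempted final evaluation would recover some data.

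Most of this stands, and it is why the point is minor. It does not remove the conflict. The plan separates leaving the study from leaving the drug, so the sentence cannot be read as a synonym. The final evaluation is only attempted and need not fall at Month 6.

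A reader might infer more than the documents support:

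- **That the conflict covers every severe adverse event.** The sections that continue follow-up address intolerance and do not expressly cover all severe events. The protocol defines severe as incapacitating, and it allows withdrawal of patients who cannot comply with procedures.
- **That more patients would be lost on mexiletine, or that false positives would rise.** No document gives withdrawals by arm or cause, and the bias is zero when the drug has no effect.
- **That the missing-data analysis is itself wrong.** The plan states its assumption openly: "A key assumption underlying this analysis is that the missing data are" missing at random. The multiple imputation rests on the same assumption. A delta-adjusted or placebo-based analysis would be a reasonable extra, but this wording conflict does not require it.

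**Conclusion.** The inconsistency is real and confined to one sentence and one trigger. Followed literally, the sentence ends follow-up of patients whom the rest of the plan would keep. The Month 6 effect would then be overstated by at most about 9 ft for one mexiletine loss and 18 ft for two, against a design effect of 183 ft.

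Those bounds assume 20 per arm, SD 190 ft, a true on-drug effect of 183 ft, and patients off drug who walk no better and no worse than placebo patients. Two losses for intolerance alone would use up the whole 10% allowance, so that is an upper case, not an expected one. The precision to be gained from full follow-up is small. This is a minor flaw in conduct wording that should be corrected. The planned analysis is not in error.

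**What to change.** Replace the one sentence in the risk section with wording such as:

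> Patients with intolerable side effects will have study medication reduced or stopped as described under Withdrawal/ Discontinuation/ Dosage Reduction. Patients with severe adverse events, as determined by the PI, will have study medication stopped; Level Three cardiac events follow the DSMB rule under Measurement of Cardiac Conduction Defects. All will continue to be followed per protocol if willing and medically able.

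Severe events get stoppage, not dose reduction alone. The cardiac rule (temporary stoppage until the DSMB decides) is left intact. The medical-ability exception matches the plan's existing allowance for patients who cannot comply with procedures.

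The cost is one sentence of protocol text and some visits for patients already off drug. The estimate will then include those patients, as the intention-to-treat plan already intends. If 2 of 20 lose all benefit, the effect being estimated is 183 × 18/20 = 164.7 ft. Power with 20 per arm is then about 0.76, or about 0.75 once the extra spread in the mexiletine arm is counted, against the planned 0.80 for 183 ft. No change to the analysis is required.

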### **Study Testing Procedures:**

#### Evaluation of safety and tolerability:

Adverse side effects will be monitored during each CRC visit (Baseline, Month 3, Month 6) and during telephone calls at about 2 week intervals during the intervening weeks of the trial. The adverse effects of mexiletine observed most commonly include: dizziness, lightheadedness, nervousness, nausea, vomiting, or upset stomach, diarrhea, constipation, trembling, shaking of hands, blurred vision, tiredness, or weakness. More serious side effects, which are less common include: irregular heart beat, chest pain, shortness of breath, trouble breathing, skin rash, severe itching, or hives.

If there are more serious side effects, the principal investigator will be notified. The principal investigator will contact the patient and determine if it is necessary to have the patient reduce the dosage of treatment agent or to stop it. The principal investigator will also determine if an urgent evaluation of the patient is necessary. These medical plans and any related change in care will be coordinated with the primary care physician of the patient. If necessary, the code will be broken to determine if the patient is receiving placebo or mexiletine treatment.

Additional details regarding the evaluation of the safety and tolerability of this medication are provided in the human subjects section of this application.

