#### Analysis of Safety Outcomes and Subject Disposition:

Adverse events will be tabulated by treatment group, severity, and perceived relationship to study drug. For each adverse event (AE), the treatment groups will be compared regarding the occurrence of at least one event using Fisher's exact tests. The comparisons will be repeated excluding all mild symptoms. Particular attention will be paid to AEs known to be associated with mexiletine in previous studies. Individual AEs will be listed, with particular attention paid to serious AEs. Laboratory test abnormalities will be similarly analyzed, whether or not they are judged to be clinically significant (classified as AEs).

Continuous measures of safety (vital signs, EKG results, laboratory test results) will be analyzed descriptively. Formal analyses may be performed using methods similar to those described above for the primary outcome variable (repeated measures analysis of covariance).

The frequency of and reasons for subject withdrawal, dosage reduction, and premature withdrawal of study drug will be summarized by treatment group. The compliance data (amount of unused drug returned, compliance diaries) will be summarized by treatment group and visit, as will dosage level of study drug. Guessed treatment from the blindness questionnaire will be tabulated by actual treatment separately for subjects and the investigator. Chi-square tests will be used to determine whether or not the proportion of subjects who guess that the subject received mexiletine treatment differ among the actual treatment groups. The investigator's guesses will be similarly analyzed. Additional information regarding adverse event assessment and processing is provided in the Human Subjects Protection portion of this application.

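### The protocol gives different study drug instructions for intolerance, and for surgery, illness or inability to undergo procedures, in Sections D and E, with no stated order or precedence

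*Combined protocol and SAP*

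**What the plan says.** Three places in the protocol say what happens to study drug when a patient has difficulty.

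- **Section D, Withdrawal/Discontinuation/Dosage Reduction.** On intolerance: "If a patient experiences intolerable adverse events, the dosage may be reduced by one level". The next sentence accepts that some patients will come off drug: "Patients who experience intolerable adverse events requiring withdrawal of study medication or who require treatment with exclusionary medications will continue to be followed", if they are willing. On surgery, illness and procedures: "Patients may also be withdrawn because of an inability to comply with study procedures (e.g., because of significant surgery or medical illness".
- **Section D, Evaluation of safety and tolerability.** For side effects that the protocol classes as more serious, the principal investigator is to "determine if it is necessary to have the patient reduce the dosage of treatment agent or to stop it". This subsection refers the reader to the human subjects section for further detail on safety and tolerability.
- **Section E, Procedures for Protecting Against or Minimizing Risks.** "Patients will be withdrawn from the study if intolerable side effects or severe adverse events, as determined by the PI, are identified". The sentence after it reads: "Patients who cannot tolerate the medication or procedures, have surgery or other illnesses which affect the evaluations will have the drug discontinued".

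Two analysis passages depend on these rules. Statistical Analyses says: "If a subject cannot tolerate or refuses to continue taking study medication, we will continue to follow and evaluate that subject", again subject to willingness. Analysis of Safety Outcomes and Subject Disposition says: "The frequency of and reasons for subject withdrawal, dosage reduction, and premature withdrawal of study drug will be summarized by treatment group".

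**The concern.** Section D makes dose reduction an option for an intolerant patient. Section E has no reduction step and words discontinuation as mandatory. For surgery, illness or trouble with procedures, Section D allows withdrawal at discretion and is silent on the drug, while Section E requires that the drug be stopped.

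Two things are at stake. Tolerability is a secondary aim, and the counts of reductions and discontinuations by group are part of how it will be reported. If staff can follow either section and still be within protocol, those counts partly measure the choice of section. Second, the primary analysis is by intention to treat at Month 6, so the treatment that mexiletine patients are actually taking by then affects the difference being estimated.

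**Working it through.** **Side-by-side reading**

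| Situation | Section D | Section E, risk procedures |
|---|---|---|
| Drug not tolerated | One-level reduction permitted; stopping also foreseen, with follow-up continued | Withdrawn from the study; drug discontinued; no reduction step |
| More serious or severe events | Principal investigator chooses between reducing and stopping | Withdrawn from the study once the principal investigator identifies the event as severe |
| Surgery, illness, procedures | Withdrawal optional; no drug rule | Drug discontinued, mandatory |

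The first and third rows concern essentially the same situations and differ in what is permitted and what is required. The second row is looser, because more serious side effects and severe adverse events are not defined as the same category, but discretion on one side still meets mandatory wording on the other. Neither section refers to the other on order or precedence. Section E is operative text, since Section D sends the reader to it. The protocol elsewhere expects reductions to occur: the adverse event items in Section E's reporting plan include a reduced dose as a recorded action, and the disposition analysis tabulates reductions.

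**The plan's own power figure**

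Inputs from Sample Size Considerations: difference 183 ft, SD 190 ft, 18 per group, 80% power. That statement gives no significance level. Two-sided 0.05 is assumed, as stated there for the secondary outcomes.

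- Standard error = 190 × √(2/18) = 63.33 ft; noncentrality = 183/63.33 = 2.889; df = 34; critical t = 2.032.
- Noncentral t power = 80.2% (79.9% at the final-analysis level of 0.049). The stated figure reproduces.
- 18/(1 − 0.10) = 20 per group, as stated.

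**Illustration of what the choice of rule could do**

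The following assumptions are not in the documents. Of 20 mexiletine patients, k are affected. A stopped patient keeps none of the effect at Month 6. A patient reduced from three to two daily doses keeps two thirds. SD and two-sided 0.05 are unchanged. All 20 per group are followed, which is what Section D and Statistical Analyses intend.

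Expected difference = 183 × [1 − (k/20) × (1 − fraction kept)]. Standard error = 190 × √(2/20) = 60.08 ft; df = 38; critical t = 2.024.

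| k of 20 | Drug stopped: difference, power | Drug reduced: difference, power |
|---|---|---|
| 0 | 183.0 ft, 84.3% | 183.0 ft, 84.3% |
| 2 | 164.7 ft, 76.2% | 176.9 ft, 81.8% |
| 4 | 146.4 ft, 66.1% | 170.8 ft, 79.1% |

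Example, k = 2 and stopped: 183 × (1 − 0.10 × 1) = 164.7 ft; noncentrality 164.7/60.08 = 2.741; power 76.2%.

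On these assumptions the gap between the two rules is 81.8 − 76.2 = 5.6 points at k = 2 and 79.1 − 66.1 = 13.0 points at k = 4.

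**The case against.** The strongest reply is that the texts can be read in sequence: reduction is tried first, and Section E applies to the patient who still cannot tolerate the drug. Section D's wording is permissive and itself foresees stopping, so both outcomes are already there. This stands as a possible reading, and it rules out saying that the passages cannot all be followed. It does not remove the problem, because Section E states no such order, and the sequential reading does not help with surgery, illness or procedures.

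A reader might also treat the more-serious-side-effects passage as a third rule for intolerance. It is not: its trigger is a different category of event, and it conflicts only in leaving to discretion what Section E words as mandatory for severe events.

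A reader might infer that Section E takes patients off drug merely because they cannot be tested, with no safety reason. The text does not go that far. It names intolerance of procedures, or surgery or illness affecting evaluations, under a heading about minimizing risk. The section on interim analyses also lists severe confounding illness or trauma as grounds for ending participation. Whether that trigger is wise is a clinical matter and is not argued here.

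Three further points reduce the practical weight. The trial has one centre and one principal investigator, which limits divergent practice. Changes in treatment must be documented on case report forms and tabulated with reasons, so some of the ambiguity could be unpicked afterwards. The sponsor's earlier seven-week trials reported good tolerability, so few patients may be affected.

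On power, the documents give no intolerance rate and no basis for dose proportionality; the earlier trials suggested a plateau in myotonia effect between 150 mg and 200 mg three times daily. The illustration also assumes that every affected patient could remain on the reduced dose. These objections stand, and the figures are illustrative for that reason.

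**Conclusion.** The inconsistency is real and is in the current text. For drug intolerance it is optional reduction against mandatory discontinuation. For surgery, illness or inability to undergo procedures it is optional withdrawal with no drug rule against mandatory discontinuation. With no order or precedence stated, the drug received and the reported reduction and discontinuation counts can depend on which section is followed.

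Section E's withdrawal of intolerant patients from the study also conflicts with the continued follow-up promised in Section D and in Statistical Analyses. That conflict bears most directly on the intention-to-treat analysis.

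A reader might infer a definite loss of power from the table above. The documents do not support one: the number affected and the fraction of effect kept are both assumed, and if intolerance is rare the effect is small. The plan's sample size calculation itself is not in question. The conclusion rests on the wording and would hold without the power figures.

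**What to change.** Reconcile the two Section D passages and the Section E passage into one rule, stated once and cross-referenced from the other places. It should:

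- state how dose reduction and discontinuation relate to each other for drug intolerance, and how more serious or severe events fit in;
- deal separately with what happens to the drug when a patient cannot complete procedures or evaluations, including after surgery or illness;
- distinguish stopping study drug from leaving the study, in agreement with the continued follow-up in Section D and in Statistical Analyses.

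The sponsor and investigator must choose the clinical content; none is proposed here. The cost is protocol wording, with no change to sample size, visits or the primary model.
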